#### Mono-Linear and Mono-Exponential Model For TTP

##### 1) Logarithmic function:

$$TTP = e^{\alpha_{\log}} \cdot \log_{10}(t) + A_{\log}$$

The model includes one intercept defined by A and one slope defined by  $\alpha$ .

##### 2) Exponential decay upwards function:

$$TTP = A_{\exp} + B_{\exp} \cdot (1 - e^{\alpha_{\exp} \cdot t})$$

The model includes one intercept defined by A, one asymptote defined as B, and one slope defined by  $\alpha$ .

#### Mono-Linear, Mono-Exponential and Bi-Exponential Model For CFU

##### 1) Mono-linear model:

$$\text{Log10CFU} = A_{\text{mono}} - \alpha_{\text{mono}} t$$

##### 2) Bi-linear (Step function) model:

$$\text{Log10CFU} = A_{\text{bi}} - \alpha_{\text{bi}} t \quad \text{where } t \leq k$$

$$\text{Log10CFU} = A_{\text{bi}} - (\alpha_{\text{bi}} - \beta_{\text{bi}})k - \beta_{\text{bi}} t \quad \text{where } t > k$$

The models will include one intercept defined by A and one or two slopes defined by  $\alpha$  and  $\beta$  and k the node parameter.

### 3) Mono-exponential model:

$$\text{Log10CFU} = \text{Log10}(e^{A_{\text{mono}} \cdot e^{-\alpha_{\text{mono}} \cdot t}})$$

### 4) Bi-exponential model:

$$\text{Log10CFU} = \text{Log10}(e^{A_{\text{bi}} \cdot e^{-\alpha_{\text{bi}} \cdot t}} + e^{B_{\text{bi}} \cdot e^{-\beta_{\text{bi}} \cdot t}})$$

The models will include one or two intercepts defined by A and B and one or two slopes defined by  $\alpha$  and  $\beta$ .

## 10.3.2 Stochastic model (Random Effects)

### 1. Inter-individual variability

During the course of the model development, the Inter-individual (IIV) parameters will be tested on the structural parameters of the EBA models. Inter-individual parameters will be included in an exponential manner to ensure that the individual EBA parameters have a lower bound of zero:

$$P_i = \text{TVP} \cdot e^{\eta}$$

where TVP is the typical (Expected) value of the parameter P,  $P_i$  is the individual value of the parameter and  $\eta$  is a normally distributed random variable with mean 0 and standard deviation  $\sigma$ . Not all parameters need to be associated with IIV.

If the distributions of the  $\eta$ s are markedly non-normal, transformations of  $\eta$ s may be considered. Terms to describe correlations between  $\eta$ s will also be considered if indicated by the data. Initially, IIV should be added to the baseline only. IIV in other parameters should be explored after the treatment effect evaluation.

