#### **4.3 Sample Size Determination**

This is a proof-of-concept study without hypothesis testing. The planned sample size of 15 participants per treatment group is in keeping with other phase 2 trials of this type and accounts for the possibility of up to 3 dropouts per arm which, based on previous studies of this type conducted at these sites, represents a conservative estimate of the expected drop-out rate. Previous EBA studies indicate that a sample size of 12 participants per arm allowed for the identification of proof-of-concept i.e., change in TTP/ CFU compared to no change in TTP/CFU for all evaluated arms.

Fifteen individuals per treatment arm is a standardized sample size for EBA studies and is expected to show any potential effect of the studied drug on EBA. However, a difference in EBA between arms may not be detected if the effect difference is small. The suggested sample size of 15 individuals in conjunction with analysis using mixed effects models has previously been shown to be adequate for the assessment of EBA.

Using 12 participants per arm, a power of 80%, alpha of 0.05, and a between-patient variability in (time-to-positivity) TTP slope of 22% (coefficient of variation), will allow for the detection of EBA-TTP0-14days of 0.0483 hours, corresponding to TTP-EBA0-14days of 11 hours, using a nonlinear mixed effects model (Boeree, M. J., et al, 2015).

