22 JUL 2024

in the Trial Steering Committee Charter.

In order to progress to Stage 2, the following minimum should be met:

- RESP301 tds active treatment arm EBATTP(0-14): the predicted rate of change in the TTP in sputum over the period day 0 to 14 must be statistically different from zero at the 5 % level (demonstrating acceptable EBA to continue to Stage 2).
- $\leq 50\%$  of the participants experienced a grade 3 or higher AE.

A protocol amendment will be considered if the following safety and tolerability criteria are met:

- $\geq 25\%$  of the participants experienced a grade 2 or higher AE of any description considered probably or definitely related to IP.
- $\geq 20\%$  of the participants experienced a grade 3 or higher AE reflecting intolerance to IMP (gastrointestinal: diarrhoea, nausea, or dyspepsia; respiratory: bronchospasm).

The safety, tolerability, and EBA interim analysis will be conducted as described in Sections 10.1, 10.2, and 10.3 of this SAP respectively.

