### **10.3.6 Model discrimination**

The discrimination between models will mainly be made based on the inspection of graphical diagnostics and changes in the objective function value (OFV) and Akaike information criterion (AIC). The differences in OFVs are nominally  $\chi^2$  distributed and a difference of -3.64 corresponding to approximately a p-value of  $< 0.05$  for one degree of freedom, provided that the models are hierarchical. Preferably this should also demonstrate improvements in the graphical diagnostics and not lead to a high ( $>1000$ ) conditional number.

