### **10.3.8 Final model**

A final model should provide a good description of the observed data, not have any important trends in the relevant GOF diagnostics, have a successful termination of the covariance step and preferably have a condition number less than 1000. Should a model be accepted as final without these criteria being met, it will be discussed and justified in the report.

There will be one final model for each of the endpoints.

Based on the final EBA models for TTP and CFU, mean bactericidal activity per treatment arm will be expressed as the daily change in TTP and CFU from day 0 to day 14. If required, periods from 0 to 2 days, 0 to 7 days, 7-14 days, or any other period will be predicted or calculated as well as the 95% Bayesian credibility interval using only the patient data included in the study. Clinical trial simulations ( $n= 1000$ ) will be used to predict mean (95% prediction interval) bactericidal activity for different treatment arms and different characteristics depending on the covariates included in the final models.

Early bactericidal activity data definition table (DDT): A separate data specification table will be created for EBA. The dataset should be in excel csv format. A readme file describing the dataset column names should be created with an example for 1 participant.

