| 14.4.9  | EBA | Model | Median and interquartile range of observed EBA for 0-2, 0-7, 0-14 days, 0-15 and 14-15 days in CFU and TTP | S       |
| 14.4.10 | EBA | Model | Parameter estimates for the final CFU model  | S       |
| 14.4.11 | EBA | Model | Expected model predicted EBA for 0-2, 0-7, 0-14 days, 0-15 and 14-15 in CFU                                | 14.4.9  |
| 14.4.12 | EBA | Model | Expected model predicted daily EBA in CFU  | S       |
| 14.4.13 | EBA | Model | Individual model predicted EBA for 0-2, 0-7, 0-14 days, 0-15 and 14-15 in CFU                              | 14.4.9  |
| 14.4.14 | EBA | Model | Individual model predicted daily EBA in CFU  | 14.4.12 |
| 14.4.15 | EBA | Model | Parameter estimates for the final TTP model  | 14.4.10 |
| 14.4.16 | EBA | Model | Expected model predicted EBA for 0-2, 0-7, 0-14 days, 0-15 and 14-15 in TTP                                | 14.4.9  |
| 14.4.17 | EBA | Model | Expected model predicted daily EBA in TTP  | 14.4.12 |
| 14.4.18 | EBA | Model | Individual model predicted EBA for 0-2, 0-7, 0-14 days, 0-15 and 14-15 in TTP                              | 14.4.9  |
| 14.4.19 | EBA | Model | Individual model predicted daily EBA in TTP  | 14.4.12 |
| 14.4.20 | EBA | Model | Overview of the analysis dataset per treatment arm   | S       |

RESP30X-EBA: Statistical Analysis Plan22 JUL 2024

| 14.4 EBA General Figures |            |             |                                |   |                           |
|--------------------------|------------|-------------|--------------------------------|---|---------------------------|
| Figure number            | Population | Biomarker   | Objective                      | Table Title   | Shell References to Shell |
| 14.4.1                   | EBA        | CFU         | Outlier                        | Log 10 CFU Cleveland dotplots                                     | S                         |
| 14.4.2                   | EBA        | CFU         | Outlier                        | Log 10 CFU Repetition 1 vs Repetition 2                           | S                         |
| 14.4.3                   | EBA        | CFU         | Outlier                        | Individual Mean CFU versus mean TTP                               | S                         |
| 14.4.4                   | EBA        | CFU and TTP | Outlier                        | Individual Log 10 CFU and DVTT over Time per subject(to be added) | S                         |

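### The random-effects plan in SAP 10.3.2 does not suit the SAP 9 test of zero TTP rate: slope variability is either left out or entered in a form that cannot cross zero

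*SAP*

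**What the plan says.** **Random effects (SAP 10.3.2).** Each individual parameter is P_i = TVP·e^η, with η normal, mean 0 and SD σ. The stated reason is: "Inter-individual parameters will be included in an exponential manner to ensure that the individual EBA parameters have a lower bound of zero". The same section adds: "Not all parameters need to be associated with IIV." It then gives the order of work: "Initially, IIV should be added to the baseline only. IIV in other parameters should be explored after the treatment effect evaluation." Transformations of η may be considered if its distribution is markedly non-normal.

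**Gate (SAP 9).** For the tds arm, the predicted rate of change in TTP over days 0 to 14 "must be statistically different from zero at the 5 % level". The interim EBA analysis is referred to SAP 10.3. No test statistic is named.

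**Candidate tests.** SAP 10.3.6 says, for choosing between models, "The differences in OFVs are nominally" chi-square distributed, and prints a threshold of 3.64. SAP 10.3.8 mentions a "95% Bayesian credibility interval using only the patient data included in the study". Neither is tied to the gate.

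**Structural model (SAP 10.3.1).** In the first printed TTP function, the coefficient of log10(t) is e^α.

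**Scale (SAP 4.3).** With 12 participants per arm, 80% power, alpha 0.05 and a 22% coefficient of variation for the TTP slope, the detectable effect is given as 0.0483 hours, said to correspond to 11 hours over days 0 to 14.

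**The concern.** The gate asks whether the average rate in one arm is zero. A sound test lets participants vary around that average in both directions, including when the average is zero. The SAP offers two routes, and neither does this.

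- **Baseline-only variability.** All participants in an arm share one slope. Real differences between slopes are then treated as residual noise, and the standard error of the arm's rate is too small.
- **Exponential slope variability.** Every slope carries the sign of TVP, and the slope variance shrinks to zero with TVP. The hypothesis that the rate is zero becomes the hypothesis that no participant changes. If slopes scatter around zero, the model can describe the scatter only by moving TVP away from zero.

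This gate is the only activity criterion for proceeding to Stage 2, and Stage 1 has no inactive comparator. A false pass would commit 55 further participants. The same form also shapes Table 14.4.18 ("Individual model predicted EBA for 0-2, 0-7, 0-14 days, 0-15 and 14-15 in TTP"): with exponential slope variability, all individual predictions in an arm would move in one direction.

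**Working it through.** **1. The plan's own figure.** SAP 4.3 gives a CV but no mean slope, so only a relative effect can be derived: (1.96 + 0.84) × 0.22 / √12 = 17.8% of an unstated mean (one-sample). The 0.0483 cannot be reproduced. As hours per day it gives 0.0483 × 14 = 0.68 h, not 11 h. I therefore take the scale from the 11 h: 11 / 14 = 0.79 h/day.

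**2. What the exponential form implies.** For P_i = TVP·e^η:
- the sign of P_i is the sign of TVP for every participant;
- SD(P_i) = |TVP| · e^(σ²/2) · √(e^(σ²) − 1).

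With a 22% CV, the slope SD is about 0.17 h/day at 0.79 h/day, about 0.02 at 0.1 and exactly 0 at 0. The arm mean is TVP·e^(σ²/2); TVP itself is the median.

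**3. Type I error when slope variability is left out.** Let r = between-participant slope SD / standard error of one participant's slope. The estimated common slope then has 1 + r² times the variance the model assumes, so the error rate is 2Φ(−1.96 / √(1 + r²)):
- r = 0.5: 2Φ(−1.753) = 8.0%
- r = 1: 2Φ(−1.386) = 16.6%

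**4. Simulated rejection rates.** Assumptions: 15 participants, true slopes normal with mean zero, a free intercept per participant, residual variance known, 1,000 trials per cell (Monte Carlo error about 0.7 points at 5%).

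| Test at nominal 5% | r = 0 | r = 0.25 | r = 0.5 | r = 1 |
|---|---|---|---|---|
| Baseline-only variability | 5.5% | 6.3% | 9.4% | 16.4% |
| Exponential, likelihood ratio at 3.84 (1 df) | 6.5% | 7.6% | 12.8% | 35.7% |
| Exponential, likelihood ratio at 5.99 (2 df) | 1.6% | 2.2% | 4.4% | 21.5% |
| Exponential, Wald on TVP | 3.9% | 3.9% | 4.3% | 4.5% |
| Exponential, Wald on arm mean | 5.4% | 5.9% | 9.5% | 19.3% |
| Additive, likelihood ratio at 3.84 | 3.9% | 4.3% | 5.4% | 6.8% |

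A separate simulation gave about 10% and 38% for the exponential 1-df test at r = 0.5 and r = 1, hence the ranges 10–13% and 36–38%. With 12 participants the pattern is the same.

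**5. What r might be.** The documents do not give it. Assume a residual SD of 10 to 30 h and 15 daily samples, so that the sum of squared day deviations is 280. One participant's slope then has a standard error of 10/√280 = 0.60 to 30/√280 = 1.79 h/day. With slope SD 0.22 × 0.79 = 0.17 h/day, r = 0.29 to 0.10. The error rate is then about 5–6% with baseline-only variability, and about 6.5–8% with the exponential 1-df test, which is already 6.5% at r = 0.

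**6. What r = 0.5 and r = 1 would mean.** Over 14 days they correspond to slope SDs of 4.2 h and 8.4 h at a residual SD of 10 h, or 12.5 h and 25 h at 30 h.

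**7. The logarithmic TTP function.** e^α is positive for every finite α. Its coefficient cannot be zero or negative, and an interval for it can never include zero, whatever random effects are used.

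**The case against.** The strongest case on the other side has five parts.

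- **Order of work.** The SAP does not impose exponential variability on the slope when the treatment effect is evaluated; it starts from the baseline only. This is correct. At that step any inflation comes from omitted slope variability, not from the exponential form. It does not rescue the gate, because omission inflates the error too.
- **Unnamed test.** A Wald test on TVP holds its level, and the OFV rule is written for model selection. Also correct. But no document selects that Wald test. SAP 10.3.8 reports mean activity per arm, and a Wald test on that mean does not hold its level.
- **Degrees of freedom.** Removing TVP also removes σ, so a 2-df cut-off is arguable. It brings the rate at r = 0.5 down to 4.4%, but leaves 21.5% at r = 1.
- **Size.** The plan's own 22% CV points to small r. At those values the inflation is indeed slight. However, multiplying a CV by an active slope assumes that spread scales with activity, which is the point at issue. A CV is undefined at a zero mean.
- **Other safeguards.** Observed EBA summaries (Table 14.4.9), individual TTP plots (Figure 14.4.30), goodness-of-fit plots and visual predictive checks are planned and may expose misfit. They do not set the gate's error rate.

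The option to transform η does not help: any real η inside e^η still gives slopes of one sign.

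**Conclusion.** The concern holds as a mismatch between the variability model and the gate. If slopes vary materially around a zero mean, the level is not protected under baseline-only variability (about 8% at r = 0.5, 17% at r = 1). Nor is it under exponential slope variability tested by a 1-df likelihood ratio (about 10–13% and 36–38%) or by a Wald test on the arm mean. These sizes rest on normal slopes, linear TTP and an r that the documents do not state. At the r of 0.1–0.3 suggested by the 22% CV and the assumed residual SDs, the inflation is small.

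A reader might infer more than this, and the documents do not support it:
- that the gate is bound to over-reject: no statistic is named, and one candidate keeps its level;
- that error rates above 30% are to be expected: r = 1 would need a slope SD of 0.60–1.79 h/day, or 76–228% of the 0.79 h/day rate, and nothing in the documents points there;
- that the qd or bd arms could be declared active by the same test: the 5% criterion covers only the Stage 1 tds arm, and SAP 4.3 plans no hypothesis testing;
- that worsening participants would vanish from the report: the observed displays would still show them.

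The change is worth making because it is cheap and protects the only activity criterion for Stage 2.

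**What to change.** For the SAP 9 gate, amend SAP 10.3.1, 10.3.2 and 9 as follows:

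1. Model TTP with a natural-scale slope and additive normal variability, slope_i = TVP_arm + η_i, with TVP_arm free in sign. Protocol 1.2 already allows linear functions, although SAP 10.3.1 prints none for TTP.
2. Include that slope variance when the gate is tested, and keep it in both models, with and without TVP_arm.
3. Name that comparison as the gate's test: 5%, two-sided, OFV difference of 3.84 for 1 df. The 3.64 printed in SAP 10.3.6 corresponds to p = 0.056.
4. In the TTP logarithmic function, replace e^α with an unrestricted coefficient. Additive η on α would still leave e^α positive.
5. Keep exponential variability for the baseline only, and drop the zero lower bound as an aim for rates of change.

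The cost is SAP wording and a small change to the model code. The interval for an arm's rate may be slightly wider, and a clearly active arm such as HRZE may be fitted slightly less neatly. The additive test is not exact at this sample size (6.8% at r = 1), so a short type I error simulation should accompany the change.

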## 10.3.3 Residual unexplained variability (Random Error)

The aim of the residual unexplained variability (RUV)/random error model is to ensure that the individual weighted residuals (IWRES) are approximately homoscedastically distributed across all predictors (e.g., time, occasion, and study). The RUV describes the differences between the observations and the individual predictions (IPRED)/estimates of the model. The RUV model can be either additive (homoscedastic), log-additive (exponential), proportional (heteroscedastic) or combined additive and proportional error model. The different RUV models will be evaluated for the models.

## 10.3.4 Covariate model (Mixed Effects)

After confirmation of the structural and stochastic EBA models a covariate analysis will be done. The median of baseline values of the covariate will be used for time-independent covariates. For time-dependent covariates, the actual value of the covariate at the time of the observation will be used (or closest in time to the observation). The inclusion of time-dependent covariates in the covariate analysis will be informed by the exploratory data analysis. For time-varying covariates to be included in a model there must be a clear rational for assuming that the time variation is independent of the drug treatment and not vice versa. Time-varying covariates

for which the causality is unclear may be investigated after the assessment of other covariates or drug effects.

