## 10.3 Early Bactericidal Activity (EBA)

The below provides a summary of the general planned EBA analysis, however, more elaborate model definitions and methodology will be provided in the EBA statistical report as EBA modelling is subject to the EBA data.

Exploratory graphical analysis of CFU and TTP data versus time following drug treatment. Covariate distributions will be inspected for the identification of potential outliers and to inform the analysis.

Development of population EBA models for CFU and TTP

- a) Evaluation of structural and stochastic models to describe CFU and TTP versus time profiles
- b) Investigation and characterization of covariate relationships that influence initial bacterial load and bacterial killing.

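### The Stage 1 go/no-go slope is read from a model built after an open-ended covariate search, so with 20 participants the 5% test does not hold its stated level

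*SAP*

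**What the plan says.** SAP 10.3 lists as a modelling step "Investigation and characterization of covariate relationships that influence initial bacterial load and bacterial killing", so covariates may act on the slope as well as on the starting load. SAP 10.3.4 fixes the order: "After confirmation of the structural and stochastic EBA models a covariate analysis will be done". SAP 10.3.6 chooses between models mainly on graphical diagnostics, the objective function value (OFV) and AIC. Its only numerical cut is an OFV drop of 3.64, which it equates with roughly the 5% level.

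SAP 10.3.8 states: "There will be one final model for each of the endpoints". It then reads off the result: "Based on the final EBA models for TTP and CFU, mean bactericidal activity per treatment arm will be expressed as the daily change" over the 14 days. Its simulated predictions vary "depending on the covariates included in the final models", which confirms that searched covariates can be part of the final model.

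SAP Section 9 carries this to the interim: "The safety, tolerability, and EBA interim analysis will be conducted as described in Sections 10.1, 10.2, and 10.3 of this SAP respectively". No exception is made for 10.3.4. The activity criterion for opening Stage 2 is that the tds-arm TTP slope "must be statistically different from zero at the 5 % level".

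The SAP names no candidate covariates, maximum number of terms, backward step or stricter entry level. It does not ask for a covariate-free EBA, either as the primary estimate or as a sensitivity estimate.

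**The concern.** When terms are chosen because they fit the data in hand, the selected model understates its own uncertainty. Chance covariates on the slope absorb between-participant variance and can also move the fitted arm slope. The usual test then treats the model as if it had been fixed in advance. With 20 participants there is little data to protect against this.

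The decision at stake is whether 55 more participants are enrolled. If the slope test rejects a true zero more often than 5% of the time, Stage 2 can open on activity that is partly a product of model selection. The same mechanism could narrow the primary EBA intervals at the end of the study, but with 75 participants it has far less room to act.

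**Working it through.** **Inputs.** Stage 1 has 15 tds and 5 HRZE participants, and the full study has 75 (SAP 4.1, 4.2). The gate level is 5% (SAP 9). No direction is stated, so two-sided is assumed. The OFV cut is 3.64 (SAP 10.3.6). The number of candidates is not given, so three values are used:
- 7, the covariates in the planned EBA figures of SAP 11.3 (sex, age, BMI, cavitation, extent, sputum quality, Xpert positivity);
- 15, an intermediate value;
- 28 or 29, all participant or sample characteristics in the SAP 7.1 dataset table, with baseline load counted once or twice.

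**Step 1, the plan's own threshold.** For chi-square on 1 df, P(X > 3.64) = 0.0564. The 5% point is 3.84. The stated cut is slightly looser than 5%.

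**Step 2, chance of at least one false slope covariate.** For k independent noise candidates this is 1 − (1 − 0.0564)^k, which gives 33% (k = 7), 58% (k = 15) and 81% (k = 29). In simulation at N = 20, where the likelihood ratio is more liberal, the figures are 46%, 72% and 92%.

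**Step 3, false-go rate of the gate.** Set the true tds slope to zero. Add pure-noise covariates to participant slopes by forward selection whenever N × ln(RSS before / RSS after) > 3.64, then test the tds slope at 5%. Results in %, from two linear approximations, A (2,500 runs per setting, simulation error about 0.5 to 1 point) and B:

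| N = 20 | No search | 7 | 15 | 28–29 |
|---|---|---|---|---|
| A, t test, at most 1 term | 4–6 | 8.0 | 9.2 | 14.9 |
| A, t test, at most 3 terms | 4–6 | 10.6 | 18.2 | 27.8 |
| A, t test, no cap | 4–6 | 9.7 | 20.2 | 48.9 |
| B, t test, at most 3 terms | 4 | 7 | 12 | 20 |
| A, ML z test, at most 3 terms | 7.9 | 15.2 | 25.8 | 38.8 |
| B, ML z test, at most 3 terms | 8 | 13 | 18 | 29 |

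A uses median-centred covariates, a third of them binary. Using continuous, mean-centred covariates instead brings A's t-test results for 7 and 15 candidates to about B's, so covariate coding explains most of the gap. With candidates correlated at 0.3 (A, 15 candidates, at most 3 terms) the t-test rate is 14.9%.

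**Step 4, would correcting the cut be enough?** With 3.84 instead of 3.64 (A, t test, at most 3 terms) the rates are 10.8%, 18.0% and 27.2%. It would not.

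**Step 5, full study, N = 75.** For A by t test, with 7, 15 and 29 candidates, the rates are 5.2%, 7.6% and 11.8% with at most 3 terms, and 5.8%, 9.0% and 12.4% with no cap.

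**The case against.** The strongest case on the other side has four parts.

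*Safeguards exist.* SAP 10.3.4 restricts time-varying covariates that treatment might drive. SAP 10.3.5 to 10.3.8 use goodness-of-fit plots, relative standard errors, visual predictive checks, AIC, a covariance step and a preferred condition number below 1000. These would remove some chance terms, and the simulations leave them out, so the true rates are probably lower than tabulated. None of them controls the error of the slope test.

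*The size depends on the slope model.* SAP 10.3.2 first places between-participant variability on baseline only and uses an exponential form. In a further linear check (OFV cut 3.84, at most 8 terms), false-go was 4.8%, 8.0% and 12.6% for 0, 7 and 28 candidates with no random slope, against 7.6%, 16% and 50% with normal random slopes. This stands as a limit on the magnitude. The direction is the same in both.

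*The gate is not decisive alone.* It is one minimum criterion for a steering committee that also reviews safety, in a study described as having no hypothesis testing (SAP 4.3). Observed EBA is also tabulated (Table 14.4.9). All true, but Section 9 still sets a 5% test, and the observed medians are not the criterion.

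*Stronger readings are tempting.* A reader might take the 28 dataset columns, on both load and killing, as 56 tests and infer a 1 − 0.95^56 = 94% chance of a false term, or quote only the highest false-go rates. The documents do not support this. SAP 7.1 describes a dataset, not a candidate list. Several columns overlap (BMI, height and weight; three Xpert; three spirometry), and highest SpMet comes from monitoring around dosing. Half of the 56 tests concern initial load, which is not the slope mechanism. Nor do the figures support treating the primary EBA as equally affected.

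**Conclusion.** The concern holds for the Stage 1 gate. Followed as written, the plan tests the tds slope in a model chosen by an open-ended search on 20 participants, and that test does not keep its 5% level. By t test with three or more terms allowed, false-go is about 7–11% with seven candidates and 12–20% with 15, against 4–6% with no search. A maximum-likelihood z test begins near 8% before any search and reaches about 13–15% and 18–26% with at most three terms. Searching all 28 or 29 columns gives about 20–50%, which is a worst case.

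These figures rest on a linear approximation to the mixed model, noise covariates, an assumed number of candidates, selection by OFV alone and a two-sided test. If only a favourable slope counted as a go, symmetry would roughly halve every rate, including the nominal one, and leave the relative inflation unchanged.

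For the primary EBA at 75 participants the effect is mild: about 5–6% with seven candidates and 8–9% with 15. The point should be fixed, and its weight rests mainly on the interim.

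**What to change.** In SAP 9 and 10.3.8, state that the Stage 1 gate slope and the primary EBA-TTP(0-14) come from a pre-specified model with arm effects and random effects and no searched covariates. A short fixed list, such as baseline load, is acceptable if named in advance. State the reference distribution for the gate test and make it suitable for a small sample, since the z test is already liberal without any search.

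Run the covariate search only at the end of Stage 2, label it exploratory, and report its EBA beside the primary estimate. If the interim has already been analysed, report the covariate-free slope beside the one used.

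The cost is SAP wording only. The downside is that any precision gained from a truly prognostic searched covariate is not used in the primary estimate. Data-driven choice of the structural curve (SAP 10.3.1) is a separate source of optimism, which this change removes only if the pre-specified model also fixes that curve.
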